2.7 Safety endpoints

Safety endpoints include the following:

At 75 ± 5 days following each transplant, at 365 ± 14 days following the first and last islet transplant(s), at 730 ± 14 days following the last islet transplant, and at 1095 ± 14 days following the last islet transplant:

- The incidence and severity of adverse events (AEs) related to the islet transplant procedure, including: bleeding (>2 g/dL decrease in hemoglobin concentration); segmental portal vein thrombosis; biliary puncture; wound complication (infection or subsequent hernia); and increased transaminase levels >5 times upper limit of normal (ULN)
- The incidence and severity of AEs related to the immunosuppression including: allergy; reduction in glomerular filtration rate (GFR); increase in urinary albumin excretion; addition or intensification of anti-hypertensive therapy; addition or intensification of anti-hyperlipidemic therapy; oral ulcers; lower extremity edema; gastrointestinal toxicity; neutropenia, anemia, or thrombocytopenia; viral, bacterial, or fungal infections; and benign or malignant neoplasms
- The incidence of change in the immunosuppression drug regimen
- The incidence of immune sensitization defined by presence of anti-HLA (histocompatibility antigen) antibodies absent prior to transplantation
- The proportion of subjects who withdraw from study treatment due to an organ transplant

At 365 ± 14 days following the first and last islet transplant and at 1095 days following the last islet transplant:

- The incidence of worsening retinopathy as assessed by change in retinal photography

3. Subgroup Analysis

A Subject may enter the study because she/he is having severe hypoglycemic events that require assistance or because she/he is unable to reduce HbA1c level to below 7.5% on Intensive Insulin

Statistical Analysis Plan

Therapy (see inclusion criterion 7 in the protocol). The latter group may be very small. However, if there are at least 6 subjects in each group, we will perform subgroup analyses that examine these two subgroups separately. Analyses will include all primary and secondary outcome measures and use the same analysis strategies that were used for those measures. Please note that power for these analyses will be very small but the results may lead to a better understanding of the mechanisms of outcome.

4. Sample Size and Power Calculations

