5.1.1 Study Period

The trial consists of three periods: (1) the pre-transplant period, which includes screening, enrollment, and wait list time; (2) the period that includes the islet transplant procedure(s); and (3) follow-up visits through 24 months following the last transplant. The study period of this trial is a 36-month follow-up after the final islet transplant. Subjects may undergo up to 3 transplants in the course of this study; the last transplant can occur not later than 8 months following the first transplant.

In the first period, individuals who meet the general inclusion criteria will be approached regarding participation in the study. After informed consent has been obtained, they will be formally enrolled into the study. Eligibility will be confirmed based on the results of the screening visit procedure detailed in Appendix 1 of the CIT-06 protocol. Enrolled subjects who meet the eligibility screening for the studies will be put on the waiting list for an islet transplant.

After completion of the screening assessments confirming eligibility for the study, a subject will undergo 12 months of intensive insulin therapy (IIT) by an experienced diabetologist (see Appendix 3). If a subject received at least 12 months of **intensive diabetes management** prior to enrollment and experienced at least one episode of **severe hypoglycemia** during that time, the subject would not be required to receive IIT while on study as long as they have a Clarke score of 4 or more. A subject is required to return to the study site for clinic visits every 3 months while undergoing IIT and while on the waitlist. Monthly HbA1c sampling between the required 3 month interval visits may be drawn locally, sent from the local lab to the study site and then shipped to the central lab for testing. Eligibility will be reconfirmed after 4 months of IIT and after 12 months of IIT. All eligibility assessments must be within the windows required for initial study enrollment. Once eligibility has been reconfirmed, a subject will be placed on the **wait list**. The subject will continue IIT while on the **wait list**.

Once a compatible islet preparation becomes available, a subject's eligibility will be re-confirmed and eligible subjects will begin immunosuppression therapy on Day -2 (Day 0 is defined as the day of transplant).

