14.2 Analysis of Safety Endpoints

The safety secondary endpoints in this study target AEs related to islet transplantation (transplant procedure and/or islet product) and the immunosuppression and/or infection prophylaxis.

The targeted AEs related to the islet transplantation include:

AE-IIP-1: Bleeding (>2 g/dL decrease in hemoglobin concentration)

AE-IIP-2: Segmental portal vein thrombosis

AE-IIP-3: Biliary puncture

AE-IIP-4: Wound complication (infection or subsequent hernia)

Statistical Analysis Plan

AE-IIP-5: Increased transaminase levels (>5 times ULN)

The targeted AEs related to the immunosuppression and infection prophylaxis therapy include:

AE-IP-1: Allergy

AE-IP-2: Reduction in GFR

AE-IP-3: Increase in urinary albumin excretion

AE-IP-4: Addition or intensification of anti-hypertensive therapy

AE-IP-5: Addition or intensification of anti-hyperlipidemic therapy

AE-IP-6: Oral ulcers

AE-IP-7: Lower extremity edema

AE-IP-8: Gastrointestinal toxicity

AE-IP-9: Neutropenia, Anemia, or Thrombocytopenia

AE-IP-10: Viral, Bacterial, or Fungal Infections

AE-IP-11: Benign or Malignant Neoplasms

Results will be reported for the following time points: 75 days and one year after the first and last transplant and at 2 years, and 3 years after the first and after the last islet transplant.

We will report incidence of each AEs categorized by MedDRA term and body system. Tables with relation to the islet product and to the immunosuppression will be reported. For each category, the number of resolved events will be reported. The mean, median, standard deviation and range for the number of days until the AE is resolved will also be reported. Results will be summarized using the template provided in Appendix 2.

The incidence rate of immune sensitization, defined as detection of anti-HLA antibodies at 75 ± 5 days following the first and last islet transplant and at and one year after the first and last transplant and at 2 years, and 3 years after the first and after the last islet transplants. Exact two-sided 95% confidence interval of the incidence rate will also be reported.

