14.2.1 Statistical Analyses of Adverse Events

AEs will be analyzed according to the body system described in the *CIT-TCAE* manual. Any event that appears in a body system will be categorized into one of the five severity grades according to the *CIT-TCAE* manual or the general definition of severity given in Table 7 and analyzed accordingly. For each event, we will analyze its incidence rate per 100 person-days. Suppose for each subject, the incidence of a particular event is a Poisson process with the homogeneous incidence rate λ . At the time of analysis, if a subject is only followed r days after the initiation of induction immunosuppression, the incidence of this event is distributed according to the Poisson distribution with mean $r\lambda/100$. The maximum likelihood estimate of the

Statistical Analysis Plan

incidence rate will be obtained based on data collected from the available subjects at the analysis time. The 95% confidence interval derived using the maximum likelihood estimator theory will be also reported. The results will be summarized in the table provided in SAP Appendix 4. Moreover, we will also list all the individuals who have ever had an incident of any of the AEs listed in Appendix 5 since their initiation of induction immunosuppression.

15. Interim Analyses and Safety Monitoring Analyses

The DSMB will be convened to review safety and efficacy data following National Institutes of Health (NIH) policy. When requested, formal interim analyses to assess safety and efficacy will be performed. Formal interim analyses will include distributions of endpoints, biomarkers and AEs. Additional analyses may be requested by the DSMB.

15.1 *Interim Analysis for Early Stopping*

We will use the method for interim analyses described by Emerson and Fleming (Emerson & Fleming, 1989) which is implemented in the SPlus module S+SeqTrial (TIBCO_Software, 2009) to provide cut-points for an interim analysis for futility. This module does not require specifying the timing of interim analyses and controls the overall type I and type II errors. In order to make what follows clearer we provide some notation. Let p represent the true probability of a favorable outcome in islet transplanted subjects.

The efficacy hypothesis is

$$H_{01} : p \leq 0.27 \text{ versus } H_{a1} : p > 0.27.$$

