AE-IIP-1 incidences	6 (12.5%) C11+ C12 C22 C34 C63 C66					
AE-IIP-2 incidences						
AE-IIP-3 incidences						
AE-IIP-4 incidences						
AE-IIP-5 incidences						
AE related to the immunosuppression and/or infection prophylaxis:						

Statistical Analysis Plan

AE-IP-1 incidences						
AE-IP-2 incidences						
AE-IP-3 incidences						
AE-IP-4 incidences						
AE-IP-5 incidences						
AE-IP-6 incidences						
AE-IP-7 incidences						
AE-IP-8 incidences						
AE-IP-9 incidences						
AE-IP-10 incidences						

Statistical Analysis Plan

AE-IP-11 incidences						
---------------------	--	--	--	--	--	--

+ : Patient's identification, for example C11 stands for the incidence occurring on patient number 1 at Center #1

Statistical Analysis Plan

17.4 Appendix 4 - Analysis of Adverse Events at Month # Since Transplant Eligibility Confirmation

	AE related to the islet transplantation (islet product or islet transplant procedure) or immunosuppression and/or infection prophylaxis			AE not related to the islet transplantation (islet product or islet transplant procedure) or immunosuppression and/or infection prophylaxis		
All Adverse Events	# of incidences	The incidence rate per 100 person-days (λ)	The 95 % confidence interval of λ based on MLE theory	# of incidences	The incidence rate per 100 person-days (λ)	The 95 % confidence interval of λ based on MLE theory
Body System A Grade 5 Grade 4 Event 1 Event 2 ⋮ Grade 3 Event 1 Event 2 ⋮ Grade 2 Event 1 Event 2 ⋮ Grade 1 Event 1 Event 2						

Statistical Analysis Plan

⋮						
Body System B						
Grade 5						
Grade 4						
Event 1						
Event 2						
⋮						
Grade 3						
Event 1						
Event 2						
⋮						
Grade 2						
Event 1						
Event 2						
⋮						
Grade 1						
Event 1						
Event 2						
⋮						
Body System C						
Grade 5						
Grade 4						
Event 1						
Event 2						
⋮						
Grade 3						
Event 1						
Event 2						

Statistical Analysis Plan

⋮						
Grade 2						
Event 1						
Event 2						
⋮						
Grade 1						
Event 1						
Event 2						
⋮						

Statistical Analysis Plan

17.5 Appendix 5 - Identification of Adverse Events at Month # Since Transplant Eligibility Confirmation

	AE related to the islet transplantation (islet product or islet transplant procedure) or immunosuppression and/or infection prophylaxis		AE not related to the islet transplantation (islet product or islet transplant procedure) or immunosuppression and/or infection prophylaxis	

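### The 75-day safety report omits the second of three infusions, and the person-day AE rates have conflicting time origins and no per-infusion counterpart

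*SAP*

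**What the plan says.** **75-day time point.** SAP Section 2.7 introduces its main list of safety endpoints with "At 75 ± 5 days following each transplant, at 365 ± 14 days following the first and last islet transplant(s", followed by later dates. The list covers procedure-related AEs, immunosuppression-related AEs and new anti-HLA antibodies. Section 14.2 gives the reporting times for the targeted AEs as "75 days and one year after the first and last transplant and at 2 years, and 3 years after the first" and last transplant. It uses the same first-and-last wording for immune sensitization at day 75. Section 5.1.1 allows up to three transplants, the last no later than 8 months after the first.

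**Time origin.** Section 14.2.1 sets the exposure and the model in one clause, "if a subject is only followed r days after the initiation of induction immunosuppression, the incidence of this event is distributed according to the Poisson", and then says "The results will be summarized in the table provided in SAP Appendix 4". It uses the same origin for the listing in Appendix 5. Yet Appendix 4 is headed "Analysis of Adverse Events at Month # Since Transplant Eligibility Confirmation", and Appendix 5 has the matching heading. Under Section 5.1.1, once screening has confirmed study eligibility, "a subject will undergo 12 months of intensive insulin therapy (IIT) by an experienced diabetologist". Eligibility is then reconfirmed after 4 and 12 months of IIT, and again when an islet preparation becomes available. Some subjects are exempt from IIT on study.

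**Rate model.** Section 14.2.1 assumes that "the incidence of a particular event is a Poisson process with the homogeneous incidence rate λ" and reports it per 100 person-days. Appendix 4 has a column block for events related to the islet transplantation, including the procedure. Appendices 2 and 3 show the targeted events as number and percent by grade and do not say what the percentage is of.

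**The concern.** Bleeding, portal vein thrombosis, biliary puncture and transaminase rises are expected close to an infusion, and a subject can have one, two or three infusions. The natural summary is risk per infusion in a fixed window. The analysis section drops a time point that the endpoint section defines. The person-day rate divides a short-lived risk by a long follow-up. The table headings leave open which day that follow-up starts. Section 1 says the consortium's goal is to show that the favorable outcome rate justifies the risks of the procedure and the immunosuppression, so the procedural risk should be readable directly from the planned tables.

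**Working it through.** The SAP states no AE rate, so there is no figure to reproduce. I used its own model.

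**Dilution.** With mean rλ/100 per subject, the maximum likelihood estimate is λ = 100 × events / Σr. Inputs: 24 subjects (Section 2.1); r = 75, 365 and 1095 days (Section 2.7); and, for the longest case, 1095 + about 243 = 1338 days (8 months to the last transplant plus 36 months, Section 5.1.1). Assumptions for illustration: six infusion-related events, all by day 75, and equal follow-up.

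| r (days) | λ per 100 person-days | Fall from day 75 |
|---|---|---|
| 75 | 600/(24×75) = 0.333 | 1 |
| 365 | 600/(24×365) = 0.068 | 4.9-fold |
| 1095 | 600/(24×1095) = 0.023 | 14.6-fold |
| 1338 | 600/(24×1338) = 0.019 | 17.8-fold |

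At r = 1095 the fitted constant rate expects 24 × 75 × 0.0228/100 = 0.41 events in the first 75 days, against the six assumed. The fall from day 365 to day 1095 (1095/365 = 3.0-fold) does not need every event to occur by day 75. The latest 75-day window closes at about 243 + 75 = 318 days after the first transplant, so by day 365 the count of such events is complete.

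Per infusion, the same six events are 6/24 = 25.0%, 6/36 = 16.7%, 6/48 = 12.5% or 6/72 = 8.3%. The SAP does not fix the number of infusions, hence the range. None of these proportions changes with length of follow-up.

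**Time origin.** Let W be the days from eligibility confirmation to induction; the SAP does not fix W.

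- If exposure started at eligibility, the rate would be multiplied by r/(r+W). For W = 90, 180 and 365 this is 0.80, 0.67 and 0.50 at r = 365, and 0.92, 0.86 and 0.75 at r = 1095.
- If only the table cut-off moved, month 12 would contain 365 − W = 275, 185 or 0 days after induction.
- If W is close to 0, the two origins nearly coincide.

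**Middle infusion.** Take each window as days 0 to 75 after an infusion, 76 days in all. With infusions at days 0, 90 and 180, none of the second window lies in the first or last window: 76 of 76 days are uncovered. With infusions at days 0, 30 and 105, 29 of 76 are uncovered. If k subjects have three infusions, k infusions have no 75-day report of their own. As an assumption, 2 such subjects among 36 infusions is 2/36 = 5.6%, and 8 among 48 is 8/48 = 16.7%.

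**The case against.** The strongest reply is that procedural risk is already shown undiluted. AE-IIP-1 to AE-IIP-5 go to Appendix 2 as number and percent, and Appendix 3 lists counts with patient identifiers. Appendix 4 prints the number of incidences beside each rate. That stands: a reader might infer that the whole safety report dilutes procedural risk, and it does not. Only the person-day rate is affected. What remains is that no template states a per-infusion denominator or separates first, second and third infusions.

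On the clock, the text of 14.2.1 is clear, and the safety population in Section 5.2.3 is defined by the same start of therapy. A reader might infer that month 12 in Appendix 4 would hold no treated time. That follows only if the heading means the first confirmation at screening; it could equally mean the re-check just before induction. The fault is a heading that conflicts with the text and has no single meaning.

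On the middle infusion, a reader might infer that its events are lost. The gap concerns the 75-day report of subjects with three infusions, and later reports would include those events if they are cumulative. An early second infusion is also partly covered by the first window.

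It would also go too far to say that the DSMB could not see the risk per infusion. Section 14 gives it all available AE data, and Section 15 lets it ask for more analyses.

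Finally, events over person-time is a conventional descriptive average, and no test in 14.2.1 rests on it. Splitting the rates of all other AEs into periods would leave very sparse cells in 24 subjects, so I do not recommend it.

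**Conclusion.** The point holds in three limited parts. Section 14.2 does not report a time point that Section 2.7 defines, for the second of three infusions; the number affected is unknown and is zero if nobody has three. Appendices 4 and 5 carry a different and ambiguous time origin from the text they serve; the effect on the rate runs from none to a halving at r = 365 if W reaches 365 days, and would be larger with further wait-list time. The Appendix 4 rate for infusion-related events falls mechanically: 14.6-fold from day 75 to day 1095 in the illustration, and 3.0-fold from day 365 to day 1095 for any count of events confined to the 75 days after an infusion. The six events, the equal follow-up and the values of W are assumptions. This should be corrected, but it does not undermine the safety analysis as a whole.

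**What to change.** 1. In Section 14.2, change the day-75 time point to *75 days after each transplant*, for targeted AEs and for immune sensitization, to agree with Section 2.7.
2. Retitle Appendices 4 and 5 *since initiation of induction immunosuppression*, and use that origin for both events and person-days.
3. Keep the person-day rates, and beside them report AE-IIP-1 to AE-IIP-5 as number and percent of infusions with an event within 75 days of each infusion, or until the next infusion if earlier. Give rows for first, second and third infusions, and state the denominator in the table.

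The cost is SAP and table-shell wording and a few extra rows, which will hold small counts, especially for third infusions. The calculation needs only infusion and event dates, and no clinical rule changes.

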Table 3.1 provides sample size calculations that use 27% as an estimate of the true favorable outcome rate in the IIT group. Sample sizes for alternative rates are also displayed. These were selected by using 23% (27%-2 times standard error) and 31% (27% + 2 times standard error) where the standard error is the standard error of the estimate from the DCCT study. Sample size calculations assume that an exact one sided test will be used and were calculated using the PASS (Hintze, 2011) sample size program. This table displays the sample sizes required for a one-sided 0.05 binomial test to achieve 80% and 90% power to detect true favorable outcome rates of 40%, 45%, 50%, 55%, and 60% in transplanted subjects compared to the selected rates in the IIT group. If the true favorable outcome rate at one year in IIT subjects is 27% then we would need to transplant 27 subjects to achieve 90% power to detect an improvement to 55% in transplanted subjects. We would need 19 subjects to achieve 80% power to detect 55% versus 27%. We

Statistical Analysis Plan

would need to transplant 40 subjects to ensure 90% power and 27 subjects to ensure 80% power if the true IIT rate is 31% and the true rate in islet transplant subjects is 55%.

Table 4.1: Sample sizes required to achieve 80% and 90% power

Rate in Transplanted Subjects	Power	Historic Rate - IIT		
		23%	27%	31%
40%	90%	64	113	246
	80%	46	84	175
45%	90%	39	64	105
	80%	31	46	76
50%	90%	28	39	59
	80%	21	30	43
55%	90%	21	27	40
	80%	15	19	27
60%	90%	15	19	27
	80%	12	16	17

We have chosen to transplant 24 subjects. This will provide approximately 90% power to detect a difference of 57% favorable outcome rate in islet transplanted subjects versus the estimated 27% favorable outcome rate in the DCCT population. Table 3.2 displays minimal detectable differences for sample sizes of 18, 24 and 30 subjects. With 24 subjects the smallest difference that can be detected with 90% power by a one-sided 5% level test is 57% compared to 27%. The minimal detectable difference is 52% compared to 27% with 80% power.

Statistical Analysis Plan

Table 4.2: Minimal detectable differences if the true IIT rate is 27%

	Power	
	90%	80%
18	62%	57%
24	57%	52%
30	53%	49%

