The primary aim of the analysis is to estimate the true rate of favorable outcome at one year after their first transplant in all eligible subjects for whom induction for an islet transplant is begun. The observed favorable outcome rate and a one-sided 95% exact binomial confidence interval will be used to estimate the true favorable outcome rate. The primary analysis will compute a one-sided exact binomial test of the null hypothesis that the true rate is less than or equal to 27% versus the alternative that the true rate exceeds 27% (see sample size justification). The analysis will be considered to support efficacy if the null hypothesis is rejected at the 5% level of significance. The lower bound for the confidence interval p_L will be determined as the value that satisfies the following equation:

$$0.05 = \sum_{x \geq r} \binom{24}{x} p_L^x (1 - p_L)^{24-x}$$

The rates of favorable outcome and exact one-sided 95% confidence intervals will be computed for each contributing center.

Statistical Analysis Plan

This analysis will be conducted for the ITT population. The primary endpoint should be available for all treated subjects. An exception will be if a death occurs, if the subject withdraws consent to be followed, or if immunosuppression is begun but the subject never receives a transplant. In these cases the endpoint will be classified as failure to achieve a favorable outcome. Should the endpoint not be evaluated for a particular individual for other reasons, a failure will be imputed unless an evaluation is done at a time longer than one year after transplant, in which case, that later value will be imputed. All imputations will be reported with the primary analysis. The rates and the exact one-sided 95% confidence intervals for complete data and imputed data will be compared to ascertain the sensitivity of the imputation.

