Rejecting this null hypothesis would lead to concluding that the favorable outcome rate is better than 27% in patients who receive an islet transplant. In order to ensure that the study provides the maximum safety information, this study will not be stopped for efficacy.

The futility hypothesis is

$$H_{02} : p \geq 0.67 \text{ versus } H_{a2} : p < 0.67.$$

Rejecting this hypothesis would lead to concluding that the favorable outcome rate in patients who receive an islet transplant is not greater than 0.27. The value 0.67 guarantees that the probability of a type II error (accepting the null hypothesis when it is false) is less than or equal to 0.025. That is, the probabilities of type I and type II errors are equal.

In order to illustrate the method, Table 13.1 assumes two equally spaced analyses; an interim analysis when 12 subjects have completed their one-year post first transplant visit and a final analysis when all 24 subjects have completed their one-year post first transplant visit. The table provides cut-points for a recommendation for futility (Reject H_{02}). Column 4 in this table (labeled number of favorable outcomes required) provides the largest number of observed favorable outcomes that would lead to recommending futility.

Statistical Analysis Plan

At the first interim analysis (when 12 subjects have completed the study) the monitoring plan would recommend for futility if no more than 2 of the first 12 islet transplant subjects experienced a favorable outcome at one year after their first transplant.

Table 13.1: Sequential Monitoring Plan

Patients Accrued		Fixed Sample p-value	Number of Favorable outcome Required*
12	Reject H_0	.5000	≤ 2
24	Accept H_0	.0243	<11

Source SPlus SeqTrial

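### Section 15.1 monitors the primary hypothesis as a design with equal 2.5% errors, while Sections 4 and 10.1 use an exact 5% test; the interim cut does not match its p-value and the futility conclusion does not follow

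*SAP*

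**What the plan says.** Section 10.1 fixes the primary analysis as an exact one-sided binomial test against 27%: "The analysis will be considered to support efficacy if the null hypothesis is rejected at the 5% level of significance". Section 4 sizes the trial on the same level: "With 24 subjects the smallest difference that can be detected with 90% power by a one-sided 5% level test is 57% compared to 27" percent.

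Section 15.1 monitors the same null (H01: p ≤ 0.27) and adds a futility hypothesis, H02: p ≥ 0.67. It says the choice of 0.67 ensures that "the probability of a type II error (accepting the null hypothesis when it is false) is less than or equal to 0.025", and then: "That is, the probabilities of type I and type II errors are equal". There is no stopping for efficacy.

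Table 13.1, credited to S-Plus SeqTrial, has two rows:

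- 12 subjects: reject H0, fixed-sample p .5000, at most 2 favorable outcomes.
- 24 subjects: accept H0, fixed-sample p .0243, fewer than 11 favorable outcomes.

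The text repeats the interim rule as futility if "no more than 2 of the first 12 islet transplant subjects experienced a favorable outcome at one year". On what a futility finding means, it says: "Rejecting this hypothesis would lead to concluding that the favorable outcome rate in patients who receive an islet transplant is not greater than 0.27".

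**The concern.** One null hypothesis carries two significance levels. A DSMB member reading Section 15.1 would take the monitored design to have 2.5% error on each side, while the analysis that decides the trial is an exact 5% test. If the stated errors do not belong to the tabulated rule, the board is working from the wrong operating characteristics.

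Two further items affect what the board does and reports. If the interim p-value and count disagree, it is unclear which one is the rule, and that changes how often an ineffective treatment is stopped at 12 subjects. If futility is reported as showing a rate no higher than 27%, the report claims something the data at the boundary cannot show.

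**Working it through.** **Inputs.** n = 24, null 0.27, exact one-sided test at 5% (Section 10.1); alternative 57% with 90% power (Section 4); futility value 0.67, claimed errors of 0.025, cuts of at most 2/12 and fewer than 11/24, p-values .5000 and .0243 (Section 15.1, Table 13.1).

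**1. Section 4 reproduces at 5%.** With X ~ Bin(24, 0.27), P(X ≥ 10) = 0.0862 and P(X ≥ 11) = 0.0369, so the exact 5% test rejects at 11 or more. Power at 57% is P(X ≥ 11 | 0.57) = 0.904, as stated.

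**2. Table 13.1's p-values reproduce at 2.5%.** Take a symmetric two-look design with O'Brien-Fleming-shaped boundaries, equal spacing and one-sided error 0.025. Its final critical value is z = 1.9726, and 1 − Φ(1.9726) = 0.0243. By symmetry the alternative lies 2 × 1.9726 = 3.945 standard errors from the null, so the lower bound at half the information falls exactly on the null value, giving p = .5000. At 5% the final value would be z = 1.6677, p = 0.0477. The printed p-values therefore come from a 2.5% design, not the 5% test of Section 10.1.

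**3. Exact errors of the tabulated rule.** Stop at ≤ 2/12, otherwise succeed at ≥ 11/24:

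- Type I at 0.27: Σ P(X₁ = k) P(X₂ ≥ 11 − k) over k = 3 to 12 = 0.0367 (0.0369 without the interim look).
- Type II at 0.67: 1 − 0.9904 = 0.0096 (0.0094 without the interim look).

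The errors are not equal, and type I exceeds 0.025.

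**4. Interim row.** Against 27%, p = .5000 is an observed rate equal to the null: 12 × 0.27 = 3.24, which as a count means at most 3. The printed cut is at most 2. Exact upper-tail p-values are 0.875 at 2/12 and 0.669 at 3/12. The two candidate cuts compare as follows (success at ≥ 11/24):

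| Interim cut | P(stop), p = 0.27 | Type I | Power at 57% |
|---|---|---|---|
| ≤ 2/12 | 0.331 | 0.0367 | 0.904 |
| ≤ 3/12 | 0.586 | 0.0355 | 0.896 |

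**5. Futility conclusion.** Rejecting p ≥ 0.67 establishes p < 0.67. At the interim boundary, 2/12 has an exact two-sided 95% interval of 2% to 48%. At the final boundary, 10/24 rejects p ≥ 0.67 (P(X ≤ 10 | 0.67) = 0.0094), yet its exact 95% interval is 22% to 63%. Neither excludes rates well above 27%.

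**The case against.** A reader might infer more than this: that Table 13.1 fits no design at all, that .0243 is an error because no count out of 24 produces it, or that 11/24 would be a success in one section and a failure in another. The documents do not support those readings.

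- A fixed-sample p-value from a group-sequential program is a continuous boundary value, not the exact p of an attainable count, and both printed values reproduce as such.
- The final cut is also defensible. Fewer than 11 is exactly the acceptance region of the 5% test. It also fits the 2.5% bound if the null variance is used: 24 × (0.27 + 1.9726 × √(0.1971/24)) = 10.77. With variance 0.25 the bound is 11.3. The SAP does not give the program settings, so the final cut cannot be called wrong.
- Table 13.1 accepts the null only below 11, so 11/24 succeeds under both printed rules. The fall in power at 57% to about 82% belongs to a cut of 12, which the SAP never specifies.
- A futility-only look cannot inflate type I error, and the choice between 2 and 3 moves power by less than one point. The table is offered as an illustration, and formal interim analyses are done on request.

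All of this stands and limits the consequence. It does not rescue the 0.025 and equal-error statements, which are general text outside the table. Nor does it remove the mismatch in the interim row, whose cut the text restates as what the plan would recommend, or the futility sentence.

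**Conclusion.** The point holds, with limited reach. Section 15.1 implies a 2.5% type I error where Sections 4 and 10.1 use 5%. The tabulated rule has exact errors of 3.7% and about 1.0%, so they are neither equal nor both within 0.025. The interim count does not match its p-value, and the choice matters mainly for stopping an ineffective treatment (33% versus 59% at a true rate of 27%). The stated futility conclusion does not follow from rejecting p ≥ 0.67.

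The primary decision, the sample size and control of the primary type I error at 5% are unaffected. This is a correction to stated error rates, an interim threshold and a sentence of interpretation; it does not invalidate the design.

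The exact figures assume 24 evaluable subjects and one look at 12, as in Table 13.1. The identification of the underlying design rests on numerical agreement (1.9726, .0243, .5000), because the SeqTrial settings are not stated.

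**What to change.** In Section 15.1:

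- State that the final test is the exact one-sided 5% test of Section 10.1: success at 11 or more of 24, actual size 3.7%, type II error at 0.67 about 1%.
- Remove the claim of equal errors of 0.025.
- Regenerate Table 13.1 with exact binomial operating characteristics. Reconcile the interim count with its p-value, give the stopping probability at 27% and the power at 57% for the count retained, and label each row H01 or H02.
- Reword the futility conclusion to say that the rate is below 0.67 and that the trial is unlikely to show a rate above 27%.

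The cost is a short calculation and a few lines of SAP text. The stated type I error becomes slightly less favorable (3.7% rather than 2.5%), still within the 5% of Section 10.1. Sample size and the primary analysis do not change.
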